| | 
13.1 Describe the amount, method, and timing of payments to subjects.
 
13.0 COMPENSATION FOR SUBJECTS
 
Phase 1:
 
-Hot Debriefing Participants:
 
Day One (Baseline, Immediate Debriefing, Post-Test): \$25 Amazon gift card will be sent via email after completing baseline.
 
Second Post-Test (after 24 hours of the first post-test): \$20 Amazon gift card will be sent via email after completing second post-test.
 
-Cold Debriefing Participants:
 
Day One (Baseline): \$25 Amazon gift card will be sent via email after completing baseline.
 
Following Day (Debrief and Post-Test): \$25 Amazon gift card will be sent via email after completing debrief and post-test.
 
Second Post-Test (after 24 hours of the first post-test): \$20 Amazon gift card will be sent via email after completing second post-test.
 
-Phase 2 (Qualitative Phase): \$25 Amazon gift card will be sent via email after completing the qualitative interview. Participants who choose to withdraw at anytime during the qualitative study will also receive a \$25 Amazon gift card will be sent via email.
 
Total for hot debriefing in phase 1 (\$45)
 
Total for cold debriefing in phase 1 (\$70)
 
Total of hot debriefing in phases 1 and 2 (\$70)
 
Total of cold debriefing in phases 1 and 2 (\$95)
 |

| | |
|--|--|
| | 
The cold debriefing group will need 3 days to complete phase 1, while hot debriefing will need only 2 days to complete phase 1.
 
Both the hot and cold debriefing groups have the same time for participation; however, the cold group will need to arrive 24 hours after the simulation experience. Participants in the cold group will require additional time for transportation and scheduling a different day for the research activity. Therefore, the PI will give an additional \$25 Amazon giftcard to compensate.
 |
|--|--|

| | |
|--|---|
| 
14.0 WITHDRAWAL OF SUBJECTS
 | 
14.1 Describe the anticipated circumstances under which subjects will be withdrawn by the study team from the research without their consent.
 
Because this study presents a minimal risk, it is not anticipated that any potential participants will be withdrawn from the study. In case they feel uncomfortable or distressed in the study, they can stop, take a break, and re-join. Participants have the right to withdraw themselves from the study at any time and will never be persuaded to participate in research activities that they refuse. If participants refuse any part of the study, that data will be considered missing.
 
Study participants will be withdrawn by the study team without their consent if the study team cannot contact them to complete phase 1 of the study.
 
Participating to phase 2 is optional, if a participant completes Phase 1 but cannot be contacted to complete Phase 1, their Phase 1 data will not be deleted.
 |
| | 
14.2 Describe any procedures for orderly termination.
 
The participants have the liberty to withdraw from the study at any point, and the study team can also withdraw them if they cannot be contacted. Participants can inform the PI of their decision to withdraw verbally, via voicemail, or email. If the study team is unable to contact a participant, they may receive a voicemail stating that they have been withdrawn from the study due to non-contactability.
 |
| | 
14.3 Describe procedures that will be followed when subjects withdraw from the research, including partial withdrawal from procedures with continued data collection, withdrawal of previously collected data upon request, etc.
 
Potential participants have the right to withdraw themselves from the study at any time, and will never be persuaded to participate in research activities that they refuse. If potential participants refuse any part of the study, further data collection will be stopped, and that data will be considered missing. Previously collected data will be withdrawn upon request.
 |
| | |

TEMPLATE: RESEARCH PROTOCOL

| NUMBER | ACTIVE DATE | PAGE |
|---------|-------------|----------|
| HRP-503 | 02-04-2020 | 20 of 40 |

| | |
|--|--|
| 15.0 RISKS TO SUBJECTS | 15.1 Describe the reasonably foreseeable risks, discomforts, hazards, or inconveniences to the subjects related to the subjects' participation in the research. It may be useful to include: a description of the probability, magnitude, duration, and reversibility of the risks. Consider the physical, psychological, social, legal, and economic risks. |
| | Their academic performance will not be impacted if they choose not to participate. The primary PI is not a faculty member at UC-CON and has no direct relationship with participants. They will not be expected to expose more than what they might face in a simulation experience that you are familiar with. In case they feel uncomfortable or distressed in the study, they can stop, take a break, and re-join. If they want to withdraw at any time, they can. In case of persistent stress or discomfort, the students' wellbeing center is ready to help them. |
| | 15.2 If applicable, indicate which procedures may have risks to the subjects that are currently unforeseeable. |
| | Not Applicable |
| | 15.3 If applicable, indicate which procedures may have risks to an embryo or fetus should the subject or the subject's partner be or become pregnant. |
| | Not Applicable |
| 15.4 If applicable, describe risks to those who are not subjects. | 15.5 Describe the procedures and actions taken to mitigate the risks to subjects and others. |
| | Not Applicable |
| | Their academic performance will not be impacted if they choose not to participate. The primary PI is not a faculty member at UC-CON and has no direct relationship with participants. They will not be expected to expose more than what they might face in a simulation experience that you are familiar with. In case they feel uncomfortable or distressed in the study, they can stop, take a break, and re-join. If they want to withdraw at any time, they can. In case of persistent stress or discomfort, the students' wellbeing center is ready to help them. |
| | To maintain confidentiality, a study ID number will be used instead of actual names on all research forms. All data will be kept on password-protected secure REDCap and OneDrive at the University of Cincinnati. The contact details of the participant will be stored within REDCap and Microsoft Outlook for UC. After verifying the accuracy of the transcripts, PI will proceed to destroy all digital recordings. After the analysis and distribution of data, the study will be finalized, and any identifiable information will be removed. The remaining data will be stored on a secure, password-protected research OneDrive, which only the PI and faculty advisor can access. All research data will be de-identified. Investigators' usernames and passwords are required to access the data in REDCap. |
| | The audio recordings will be held at a private place in the UC College of Nursing or in a secure virtual room. The audio recordings of a qualitative focus group will take place in a secure virtual room, only if the participants choose to conduct the interview in that setting. If the participants prefer an in-person focus group, then a secure virtual room may not be necessary. The audio recordings will be stored on password-protected secure REDCap and UC OneDrive. The transcribed interviews will be stored by the PI (in a de-identified form) on his UC OneDrive as per the as the UC data retention policy allows. Agents |

TEMPLATE: RESEARCH PROTOCOL

| NUMBER | ACTIVE DATE | PAGE |
|---------|-------------|----------|
| HRP-503 | 02-04-2020 | 21 of 40 |

of the University of Cincinnati may inspect study records for audit or quality assurance purposes. The data from this research study may be published; but participants will not be identified by name.

| | |
|--|---|
| 16.0 POTENTIAL BENEFITS TO SUBJECTS | 16.1 Describe the potential benefits that individual subjects may experience from taking part in the research. It may be useful to include: the probability, magnitude, and duration of the potential benefits. Indicate if there is no direct benefit to subjects. Do not include benefits to society or to others. |
| | They will probably not get any benefit from taking part in this study. But being in this study may improve the debriefing experience at the UC-CON. |

| NUMBER | ACTIVE DATE | PAGE |
|---------|-------------|----------|
| HRP-503 | 02-04-2020 | 22 of 40 |

| | |
|---|--|
| 17.0 DATA MANAGEMENT AND CONFIDENTIALITY | 17.1 Describe the data analysis plan, including any statistical procedures or power analyses. |
| | For quantitative phase 1, Statistical power G*Power 3.1 was used to determine sample size based on a 2-tailed, two-way repeated measure ANOVA for the design, a type I error of 0.05, a statistical power of 80% (type II error), and a large effect size of eta square .25-.99 (Faul et al., 2007). Based on the literature, a large effect size is appropriate for the use of simulation (Padilha et al., 2019; Pauly-O'Neill, 2009). Based on G*Power 3.1, the recommended sample size will be 26 participants in each group. Still, because there is a possibility that participants may withdraw from the study, the total number will be 30 participants in each group. There is a total of 183 eligible participants. |
| | 
Statistical Plan
 
The statistical analysis will be used by JMP Pro 16 software. The descriptive analysis for students' demographics will be computed to describe means, standard deviations, and frequencies. For hypothesis 1a, the appropriate statistical analysis test will be the repeated measure ANOVA to find the difference between the experimental and control group in pre and post-intervention. For hypothesis 1b, an independent t-test will be used to find the differences between the two groups in the BLS competence level. The p-value of <0.05 will be considered statistically significant, and the confidence interval will be set at 95%. If the p-value is less than 0.05, we will reject the null hypothesis; If the p-value is more than 0.05, we will fail to reject the null hypothesis. For hypothesis 2, an independent t-test will be used to compare means between hot debriefing and cold debriefing groups. DES with P-values <0.05 will be considered statistically significant.
 |
| | 
For Qualitative phase 2 , thematic analysis will be used because it is applicable to the aim of our study (Doyle et al., 2020). All transcripts will be transcribed by a transcriptionist. All transcripts will be uploaded to MAXQDA 2020, a qualitative analysis software. Two researchers will examine each interview transcript thoroughly on their own to ensure that the data is complete. The researchers then read and reread each interview individually, looking for keywords or phrases that defined participants' experiences and views of debriefing methods. We will use line-by-line coding, writing 1 or 2 words that will indicate what was stated (Creswell & Poth, 2018). Data will be coded according to their meaning and focuses on categorizing participant experiences and perceptions. Frequently recurring codes with the same content will be classified and compared consistently across transcripts. We will combine comparable and overlapping categories into a single category (theme) (Creswell & Poth, 2018).This classifying procedure will record participants' overall views of their experiences.
 |
| | 17.2 Describe the steps that will be taken to secure the data. |
| | To ensure the security of data, any paper forms containing research data will be kept in a file cabinet that is locked in a locked office. The data will be entered into either a password-protected computer, a password-protected secure REDCap database, or a password-protected secure OneDrive at the University of Cincinnati. After three years of the study's completion, all research data will be de-identified, and any contact information or links to study ID numbers will be destroyed by shredding paper documents and deleting electronic files. The identity and information about the participants will be kept confidential, except in cases where authorities need to be notified about abuse or immediate harm that may come to the participants or others. Agents of the University of Cincinnati may review study records for audit or quality assurance purposes. The research data may be published, but the participants will not be identified by their names. |

TEMPLATE: RESEARCH PROTOCOL

| NUMBER | ACTIVE DATE | PAGE |
|---------|-------------|----------|
| HRP-503 | 02-04-2020 | 23 of 40 |

To capture qualitative data, audio recordings of participant interviews will be made and stored on the University of Cincinnati's secure online course management system. Additionally, a backup recording using an encrypted audio recorder will be saved in the University's HIPAA-secure OneDrive folder. After de-identification, the transcriptions of the interviews will be uploaded to the study's secure online OneDrive folder.

17.3 Describe any procedures that will be used for quality control of data collection.

For quantitative data, access to REDCap will be restricted to the study team only. Any modifications made to the database, or the data stored in it will be documented in the comment section provided by the database. The REDCap database will automatically generate a code book that is specific to the research study. The Principal Investigator and the study team will review the initial data sets to ensure that the data collection and analysis are not affected by any issues with the instruments used. The team will hold weekly meetings to discuss and monitor the confidentiality of participant data. The study team will use REDCap to track data manipulation and user activity.

To capture qualitative data, audio recordings of participant interviews will be made and stored on the University of Cincinnati's secure online course management system. Additionally, a backup recording using an encrypted audio recorder will be saved in the University's HIPAA-secure OneDrive folder. After de-identification, the transcriptions of the interviews will be uploaded to the study's secure online OneDrive folder.

17.4 Describe how data or specimens will be handled study wide as outlined below.

17.5 What information will be included in the data or associated with the specimens?

For Phase 1:

- (A) Demographic
- (B) BLS Competence Checklist
- (C) Debriefing Tool
- (D) The Debriefing Experience Scale

For Phase 2:

The data collection will use a Semi-structured interview, the most common sort of interview used in this methodology, and it is the primary method of data collection (DeJonckheere & Vaughn, 2019). It will be included open-ended questions related to the participants' overall experience in terms of emotions, feelings, challenges, and learning. All the interviews will be conducted in a private place, and the PI will do all the interviews so the participants' interactions and questions will be consistent.

The general initial questions for the hot debriefing group are:

- (1) Tell me about your experience with simulation and what that's looked like for you?
- (2) Tell me about your experience in debriefing?
- (3) What did you like in debriefing?
- (4) How did debriefing help you to reflect on your simulation experiences?
- (5) Did you face any challenges during your experience?
- (6) What did you not like with debriefing?
- (7) How has debriefing impacted your ability to learn concepts or attain competency in your nursing skills.

TEMPLATE: RESEARCH PROTOCOL

| NUMBER | ACTIVE DATE | PAGE |
|---------|-------------|----------|
| HRP-503 | 02-04-2020 | 24 of 40 |

(8) How did debriefing impact your confidence in performing at the bedside?
 (9) Do you have any advice for educators who are designing simulation scenarios?
 (10) Is there anything else you would like to share?

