| | 
6.1 Thoroughly describe the study design.
 
This study consists of two phases. Phase 1 will be a randomized controlled trial (RCT). Having a controlled group is the gold standard to measure the efficacy of an intervention (Polit & Beck, 2021). RCTs provide the most persuasive evidence on whether one variable has a causal influence on another. RCTs' main strength is the certainty with which causal links may be determined. Kolb's learning theory serves as the underpinning for this study (Kolb & Kolb, 2009; Kolb, 1984).
 
Manipulation: The researcher will do a cold debriefing (after one-day post-simulation) for undergraduate nursing students in the intervention group.
 
Control: The control group will do a hot debriefing (immediately after the simulation).
 
Randomization: The researcher will assign the participants to a control or experimental based on number generator.
 
Once participants complete Phase 1, we will record their progress on REDCap. If they chose to only participate in Phase 1, we will mark their status as "completed" on REDCap. If they expressed interest in Phase 2, we will randomly select 16 participants from the pool based on a number generator and update their status on REDCap for Phase 2.
 
Outcome: The study outcome is BLS competence level. The competence level will be measured AHA (2020) BLS competency Checklist. First, the control and experiment groups will complete a pre-test on BLS competence. Both groups will do a pre-test. After finishing
 |

TEMPLATE: RESEARCH PROTOCOL

| NUMBER | ACTIVE DATE | PAGE |
|---------|-------------|----------|
| HRP-503 | 02-04-2020 | 10 of 40 |

the pre-test, we will do the randomization process. Then the intervention group will receive (cold debriefing); the control group will have the (hot debriefing). Both groups will do the post-test immediately after the debriefing session and another post-test after 24 hours of the first post-test.

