For phase 2, we will do a qualitative descriptive design with focus groups interview. Themes relating to hot and cold debriefing will be generated using a focused qualitative interview technique. Focused interviews are loosely structured interviews in which the interviewer guides the participant through a set of questions (Polit & Beck, 2021). Throughout the guide, participants are encouraged to share their own experiences and discuss all topics freely. Researchers can obtain all necessary information utilizing this technique, and participants will have the capability to provide illustrations and explanations (Polit & Beck, 2021).

6.2 Detail the procedures being performed, specifically the interaction or intervention with human subjects and/or their identifiable information. Please be clear and concise and provide information relevant to the current study. For example, please be sure that what will be done for this research is explained and differentiated from activities that have already taken place or will be submitted for future review. Please note that details about recruitment and consent are asked in later questions.

Potential participants will access the REDCap link to answer the eligibility questions (1) if they are above 18 years of age and (2) if they are senior or third year undergraduate nursing students. If they are eligible, they will enter their demographic on REDCap. After that, The PI will assign the participants to a hot or cold debriefing group based on a number generator. Participants will do a baseline BLS competence where they will do a simulation experience related to the competence of BLS, which is conducted as part of the study design. There will be a scenario about a nurse taking care of their client at a hospital, and when the nurse enters the client's room to check on their client, they find that their client is unresponsive. Nursing students are expected to start the process of Basic Life support. Nursing students are expected in the simulation to check the client's

TEMPLATE: RESEARCH PROTOCOL

| NUMBER | ACTIVE DATE | PAGE |
|---------|-------------|----------|
| HRP-503 | 02-04-2020 | 11 of 40 |

responsiveness, activate the cardiopulmonary arrest code, begin cardiopulmonary resuscitation, and give 30 compressions and 2 breaths. They will attach an automated external defibrillator and follow the instruction of the machine. The total scenario will last up to 5 minutes.

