Another interaction with participants will be the debriefing experiences, where students will do a group debriefing. Afterward, participants in the hot debrief group will do their post-test immediately after their debrief on the same day as the simulation, and another post-test after 24 hours of the first post-test. And then, the cold debrief participants will do the simulation, wait 24 hours, have the debrief, and will do an immediate post-test, and another post-test after 24 hours of the first post-test. The simulation will be conducted in order to complete the BLS assessment checklist at baseline, post-test, and second post-test. The same simulation and BLS Assessment checklist will be conducted at baseline, post-test, and second post-test. The BLS competence and DES will be administered online via REDCap. During the qualitative phase, participants will engage in a focus group which will be the final interaction. Random sampling will be used to select subsamples from both hot and cold groups for the focus group..

6.3 Describe procedures being performed to monitor subjects for safety or minimize risks.

The study carries minimal risk. Potential participants will not be expected to expose more than what they might face in a simulation experience that they are familiar with. Participants will be informed that they can choose to participate or not and can withdraw at any time. They can also decline to answer any questions that make them uncomfortable. The PI will receive training from the Co-PI/Faculty Advisor to monitor participants for any psychological stress during study phases. The PI and Co-PI/Faculty Advisor will meet weekly to discuss interactions with participants and ensure that the procedures for managing data protect confidentiality.

6.5 Where applicable, list and describe the data collection tools such as surveys, data collection forms, etc. All tools described should be uploaded in the RAP Smart Form on the Local Site Documents page unless they are standardized, validated tools.

For Phase 1

- (A) Demographic
- (B) BLS Competence Checklist

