The baseline BLS Competence level will be measured via the AHA (2020) BLS competency checklist. The BLS Competence assessment will be conducted by the primary investigator and/or [name] (Co-PI). All of the tests (Baseline, post-test, and second post-test) will be measured by the same tool of the AHA (2020) BLS competency checklist. The simulation will be conducted in order to complete the BLS assessment checklist at baseline, post-test, and second post-test. The same simulation and BLS Assessment checklist will be conducted at baseline, post-test, and second post-test.

- (C) Debriefing Tool
- (D) The Debriefing Experience Scale

TEMPLATE: RESEARCH PROTOCOL

NUMBER

ACTIVE DATE

PAGE

HRP-503

02-04-2020

12 of 40

| Phase 1 | | | | | | | |
|--------------------------|--|---------------------|----------|------------|---------------------|--------------------|--|
| Construct | Measure name | Minutes to complete | Baseline | Debriefing | Immediate Post test | 24-hours post-test | |
| (A) Demographics | Demographic (6 items) age, gender, Race, ethnicity, Finished credits hours, GPA, BLS certificate. | 5 minutes | X | | | | |
| (B) BLS Competence level | AHA (2020) BLS competency Checklist. there are 15 items, for each item 0 (not done or done incorrectly) and 1 (done correctly). | 5 minutes | X | | X | X | |
| (C) Debriefing Tool | The PEARLS Healthcare Debriefing Tool The tool has five domains (Bajaj et al., 2018) : (1) Setting the Scene, (2) Reactions, (3) Description, (4) Analysis, and (5) Application/Summary | 10 minutes | X | | | | |

TEMPLATE: RESEARCH PROTOCOL

| NUMBER | ACTIVE DATE | PAGE |
|---------|-------------|----------|
| HRP-503 | 02-04-2020 | 13 of 40 |

| | | | | | | | | | | |
|---------|--|--|--|------------|----|----|----|---|--|--|
| | | (D) Debriefing Experience Scale | The Debriefing Experience Scale (DES) (Reed, 2009, 2012) 20 items in total and was split into four subscales: (1) Analyzing Thoughts and Feelings; (2) Learning and Making Connections; (3) Facilitator Skill in Conducting the Debriefing; and (4) Appropriate Facilitator Guidance (Reed, 2009, 2012). The items on the scale were rated in two different areas: the "experience" for the student and the "importance" of the simulation experience (Reed, 2009). The 20 items were scored on a Likert scale of 1 (strongly disagree) to 5 (strongly agree) (Reed, 2009). | 10 minutes | X | | | | | |
| | | Total minutes | Total data collection minutes each visit | | 30 | 10 | 20 | 5 | | |

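### Protocol sections 6.1 and 6.2 put randomisation on different sides of the baseline BLS test, and the PI who allocates may also score the BLS checklist, with no concealment or rater masking described

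*Protocol*

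**What the plan says.** **Order of events.** Section 6.1 places randomisation after the baseline test: on finishing "the pre-test, we will do the randomization process". Section 6.2 takes the student through eligibility questions and demographics in REDCap and continues: "After that, The PI will assign the participants to a hot or cold debriefing group based on a number generator". Its next sentence is "Participants will do a baseline BLS competence where they will do a simulation experience related to the competence of BLS".

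**Who allocates.** Section 6.2 names the PI. Section 6.1 says "The researcher will assign the participants to a control or experimental based on number generator". A number generator is the only detail given of the method.

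**Who scores.** Section 6.5 says "The BLS Competence assessment will be conducted by the primary investigator and/or" the Co-PI, and applies the same checklist at baseline, first post-test and second post-test. The checklist has 15 items, each marked 1 if done correctly and 0 if omitted or done incorrectly.

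**Who debriefs.** Section 6.1 says "The researcher will do a cold debriefing (after one-day post-simulation) for undergraduate nursing students in the intervention group".

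**What is tested.** Hypothesis 1b (section 1.2) predicts greater competence after cold debriefing. Section 17.1 and the SAP both test it with an independent t-test, and neither states a baseline adjustment.

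The available text of the protocol and SAP contains no provision for concealing the allocation or masking the rater.

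**The concern.** The order matters for two reasons. If the group is fixed and known before baseline, the baseline score is no longer guaranteed to be independent of allocation, and baseline is one end of the pre-to-post comparison in hypothesis 1a. Staff also cannot follow both sections, so the order actually used could vary from student to student.

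The overlap of roles matters under either order. The outcome is an observer's judgement of whether a skill was performed correctly. A rater who knows the group, and whose study predicts the direction of the result, can lean on borderline items without intending to. Done/not-done items narrow that discretion, but deciding whether a step was done correctly still takes judgement. The unadjusted post-test comparison for hypothesis 1b would absorb any such lean directly.

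**Working it through.** **1. The two sequences side by side**

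| Step | Section 6.1 | Section 6.2 |
|---|---|---|
| Eligibility and demographics | not placed in the sequence | first |
| Baseline BLS test | before randomisation | described after assignment |
| Randomisation | after baseline | after demographics, by the PI |
| Debriefing, then post-tests | follow | follow |

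Section 6.1 is explicit. In section 6.2 the assignment is tied to demographics, but the sentence on baseline has no sequencing word, so its position rests on narrative order. Section 6.1 is also not perfectly clean, because it speaks of control and experimental groups doing the pre-test. The natural readings still conflict.

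**2. Who can know the group at each test if the PI scores**

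| Test | 6.1 order | 6.2 order |
|---|---|---|
| Baseline | group not yet assigned | group can be known |
| First post-test | group known | group known |
| Second post-test | group known | group known |

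The order conflict therefore affects the baseline row only. The role overlap affects both post-test rows whichever order is used.

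**3. Illustration for hypothesis 1b**

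Inputs from the documents: 26 per arm (sections 3.1 and 17.1), 5% significance level, independent t-test. I take the test as two-sided, as in the sample-size statement. Assumption: the rater adds a mean shift of *s* standard deviations to one arm when there is no true difference. The documents give no SD and no rater-agreement data, so *s* is a range and not an estimate.

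- Degrees of freedom: 2 × 26 − 2 = 50; critical value 2.009.
- Noncentrality: λ = s × √(26/2) = 3.606 × s.
- False-positive rate: P(|T| > 2.009), where T is noncentral t with 50 degrees of freedom and noncentrality λ.

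| Assumed shift s | λ | False-positive rate |
|---|---|---|
| 0 | 0 | 5.0% |
| 0.1 SD | 0.361 | 6.4% |
| 0.2 SD | 0.721 | 10.9% |
| 0.3 SD | 1.082 | 18.6% |

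With all 30 enrolled per arm analysed, the last three rates are 6.7%, 11.9% and 20.8%.

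These rates describe knowledge of group at the post-test. They do not measure the conflict between 6.1 and 6.2, because baseline does not enter the unadjusted post-test comparison. I give no figure for hypothesis 1a: section 17.1 names repeated-measures ANOVA and the SAP a paired t-test, and a false-positive rate would need an assumption of no true change.

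**4. Scoring load if one person scores everything**

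Scenarios last up to 5 minutes (section 6.2). With 52 students: 52 × 3 × 5 = 780 minutes = 13 hours. With 60 students: 60 × 3 × 5 = 900 minutes = 15 hours.

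**The case against.** The best case for the plan is that the conflict is a drafting slip, that binary items leave a rater little room, and that REDCap's audit trail (section 6.6) already records later changes to scores. A rater could hardly be masked in any case. For hot debriefing, "participants in the hot debrief group will do their post-test immediately after their debrief on the same day as the simulation", whereas cold students come back the next day, so attendance alone usually gives the group away.

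Part of this stands. The 6.2 order is inferred from narrative sequence, and the proposed change reduces knowledge of group without removing it. But an audit trail catches edits, not a lenient first judgement. The limits on masking are also no reason for the allocator to score, or for baseline to be scored with group known.

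Several stronger readings are tempting and are not supported:

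- *The PI gives the cold debriefing.* A reader might infer this because 6.1 gives allocation and cold debriefing to the researcher, and 6.2 gives allocation to the PI. It remains an inference: section 17.1 refers to two researchers in the qualitative work, and part of the investigator section is missing from the available text.
- *The 6.1 order would prevent losses that differ by arm.* Cold takes three days and hot two (section 13.1). A student deterred by the longer schedule can leave after baseline just as easily, and is then equally missing from the post-test. The 6.1 order mostly moves such losses.
- *Consent may come after allocation.* The sentence in section 23.1 that mentions baseline times the information sheet, not consent. Section 24.1 puts consent before the study is conducted, and random assignment is naturally part of conducting it.
- *The order conflict uses up the attrition margin.* The 15% allowance is for attrition overall and may already include early leavers. Whether 60 is enough is a separate sample-size question.

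**Conclusion.** The point holds as a contradiction to reconcile and an avoidable overlap of roles. Sections 6.1 and 6.2 give different orders, the PI who allocates is permitted to score all three tests, and the available text describes no concealment or masking. The wording in 6.5 is permissive, so the PI may score; the documents do not show that the PI did.

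The size of any bias is unknown. The range of about 6% to 19% against a nominal 5% rests entirely on the assumed shifts of 0.1 to 0.3 SD and on 26 per arm. It applies under either order. A reader might infer that the hypothesis 1b result is biased, or that baseline was scored with group known; the documents establish neither. The change is worth making because it is cheap. My confidence that it matters in practice is moderate.

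**What to change.** **1. One order, with concealment.** Change section 6.2 to match 6.1: consent; baseline scored and locked in REDCap; then that student's allocation revealed. The list should be prepared in advance by someone other than the PI, for example the statistician on the dissertation committee (section 4.1), and hidden from the PI, rater and student until that point. The timing of the reveal must be reconciled with 6.1, which has hot debriefing follow the simulation at once, and with the group debriefing in 6.2. Holding back all allocations until a whole session has been tested should not be required, since it would delay some hot debriefings.

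**2. Separate scoring from allocation.** Reword section 6.5 so that the named Co-PI, or another existing IRB-approved team member who neither allocates nor debriefs, scores all three tests for every student, and the PI does not score. Two checks come first. Sections 10.5 and 15.1 rely on the PI not being faculty as a student safeguard, so a faculty scorer would need review. Section 6.3 also says "The PI and Co-PI/Faculty Advisor will meet weekly to discuss interactions with participants"; if that adviser is the scorer, group should stay out of those discussions until scoring is locked. Do not call this rater masked. Report as a limitation that the day of return usually reveals the group.

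**3. If data are already collected.** The SAP is written in the past tense. In that case report who scored each test, what they knew of group at the time, and whether allocation preceded baseline.

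**Cost.** Protocol wording, a lock step in REDCap and a prepared list. Scoring takes about 13 to 15 hours of the Co-PI's time, plus attendance on separate days, and allocation has to be done on the spot. No new staff are needed if the Co-PI or an existing team member can score.
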